#### 4.10 Analysis and Data Conventions

Each cohort will be analysed separately for the primary, secondary and exploratory endpoints. No formal statistical hypotheses will be conducted for this module. See [Section 4.22](#) for the justification of the sample size.

#### 4.11 Multi-centre Studies

No adjustments for centre will be performed for this module.

#### 4.12 Adjustments for Covariates

No adjustments for covariates will be done for this module.

#### 4.13 Multiple Comparisons/Multiplicity

Not applicable.

#### 4.14 Interim Analysis.

An administrative interim analysis will be conducted for Cohort A approximately 4 months after approximately 18 molecular eligible centrally confirmed evaluable for response participants have been enrolled. The assessment of key efficacy and safety will be performed. The purpose for this administrative interim is to inform internal decision making only with no planned adaptations to the study.

A futility interim analysis will be conducted for Cohort B approximately 6 months after at least 12 molecularly eligible centrally confirmed evaluable for response participants have been enrolled . The futility stopping rule for the prostate cohort will be based on the primary endpoint, composite response. CCI

CCI  
CCI

This stopping rule is for guidance only, and any decision to cease recruitment will be based on sponsor review of all safety and efficacy clinical data available. For the interim analysis, data will be analysed and summarised in an unblinded fashion as outlined in this document.

The participant disposition, key baseline characteristic and key safety outcomes will be summarised. The primary and key secondary endpoints will be summarised as specified in [Section 4.16](#) and [Section 4.17](#) respectively. The list of tables, listings and figures required for interim analysis will be prepared as per AZ standards; and they will be flagged separately in the list of tables, listings and figures (which will be a separate document) for the entire study.

An additional ‘interim analysis set’ is defined as all subjects in the ‘Molecular eligible centrally confirmed evaluable for response’ set with chance to have at least two follow up RECIST assessments. This interim analysis set will be used for the evaluation of the primary and key secondary efficacy endpoints (ORR, BoR, etc).

#### 4.15 Examination of Subgroups

The following subgroups will be analysed for the primary and secondary tumour response endpoints in this module:

- CCI
- CCI
- CCI
- CCI
- CCI
- CCI
- CCI
- CCI

#### 4.16 Primary Efficacy Variables

The primary and secondary efficacy summaries and figures will be provided only for the participants who received 160 mg BID ceralasertib as starting dose on Cycle 1 Day 1. Listings will be provided for all participants irrespective of their starting dose of ceralasertib.

##### 4.16.1 Objective Response Rate (Cohort A)

ORR is defined as the percentage of participants who have a confirmed visit response (CR or PR prior to evidence of progression (as defined by RECIST) and will be based on a subset of all participants with measurable disease at baseline.

A participant will be classified as a responder, if the RECIST criteria for a CR or PR are satisfied at any time following first dose/administration of study medication, prior to RECIST progression and prior to starting any subsequent cancer therapy. All responses of CR or PR must be confirmed.

A confirmed response of CR/PR means that a response of CR/PR is recorded at 1 visit and confirmed by repeat imaging not less than 4 weeks after the visit when the response was first observed with no evidence of progression between the initial and CR/PR confirmation visit. Data obtained up until progression, or last evaluable assessment in the absence of progression, will be included in the assessment of ORR. Participants who discontinue study treatment without progression, receive a subsequent anti-cancer therapy and then respond will not be included as responders in the ORR (i.e. both visits contributing to a response must be prior to subsequent therapy for the participant to be considered as a responder).

In the case where a participant has two non-consecutive visit responses of PR, then, as long as the time between the 2 visits of PR is greater than 4 weeks and there is no PD between the PR visits, the participant will be defined as a responder. Similarly, if a participant has visit responses of CR, NE, CR, then, as long as the time between the 2 visits of CR is greater than 4 weeks, then a best response of CR will be assigned.

The ORR will be based on the investigator RECIST data and using all scans regardless of whether they were scheduled or not.

Summaries will be produced that present the number and percentage of participants with a tumour response (CR/PR) based on molecularly eligible centrally confirmed evaluable for response set as well as evaluable for response set. A two-sided 80% confidence interval using Clopper-Pearson method will also be computed.

#### **4.16.2 Composite Response Rate (Cohort B)**

Composite Response Rate (CRR) is defined as the percentage of participants who have a composite response as defined in [section 4.9.9](#). The composite response rate will be calculated for molecularly eligible centrally confirmed evaluable for response set as well as evaluable for response set.

Data obtained up until progression, or last evaluable assessment in the absence of progression, will be included in the assessment of CRR. Participants who discontinue study treatment without progression, receive a subsequent anti-cancer therapy and then response will not be included as responders in the CRR (i.e. both visits contributing to a response must be prior to subsequent therapy for the participant to be considered as a responder).

The CRR will be based on the investigator RECIST data and all scans regardless of whether they were scheduled or not.

Summaries will be produced that present the number and percentage of participants with a composite response. A two--sided 80% confidence interval using Clopper-Pearson method will be computed for response rate.

A by module, by cohort, by subject (subject identifier, centrally confirmed NGS result and IHC level) listing of composite response components (best overall radiological response, CTC conversion status, PSA decline, overall composite response, etc) will be provided.

#### 4.17 Secondary Efficacy Variables

##### 4.17.1 Duration of Response (Cohort A)

Duration of response will be defined as the time from the date of first documented response (which is subsequently confirmed) until date of documented progression or death in the absence of disease progression (i.e., date of PFS event or censoring – date of first response + 1). The end of response should coincide with the date of progression or death from any cause used for the PFS endpoint. The time of the initial response will be defined as the latest of the dates contributing towards the first visit that was PR or CR that was subsequently confirmed.

If a participant does not progress following a response, then their duration of response will use the PFS censoring time (see [Section 4.17.3](#)).

Descriptive data will be provided for the duration of response in responding participants, including the associated Kaplan-Meier estimate of median duration of response, where there are sufficient number of responders based on molecularly eligible centrally confirmed evaluable for response set as well as evaluable for response set. A Kaplan-Meier plot and a swimmer plot will also be provided.

##### 4.17.2 Percentage change in tumour size (Cohort A and Cohort B)

Tumour size is the sum of the longest diameters (or short axis measurements for lymph nodes) of the target lesions. Target lesions are measurable tumour lesions. Baseline for RECIST is defined to be the last evaluable assessment prior to starting treatment. The percentage change in target lesion tumour size at each week for which data are available will be obtained for each participant taking the difference between the sum of the target lesions at each week and the sum of the target lesions at baseline divided by the sum of the target lesions at baseline multiplied by 100 (i.e., (week x - baseline)/baseline \* 100).

The absolute change and percentage change from baseline in the sum of tumour size at each assessment will be calculated. The best percentage change in tumour size from baseline will be the maximum reduction from baseline or the minimum increase from baseline in the absence of a reduction from baseline based on all post baseline assessments. The best percentage change in tumour size will include all assessments prior to the earliest of death in the absence of progression, any evidence of progression, the start of subsequent anti-cancer therapy, or the latest evaluable RECIST assessment if the participant has not died, progressed or started subsequent therapy. Change in tumour size at progression or the latest evaluable RECIST assessment (as applicable) should be included in the determination of best percentage change in tumour size.

If best percentage change cannot be calculated due to missing data (including if the participant has no TLs at baseline), a value of +20% will be imputed as best percentage change from baseline in the following situations (otherwise best percentage change will be left as missing):

- If a participant has no post-baseline assessment and has died
- If a participant has new lesions or progression of NTLs or TLs
- If a participant has withdrawn due to PD and has no evaluable TL data before or at PD

The best percentage change in TL tumour size from baseline will be summarised descriptively for molecularly eligible centrally confirmed evaluable for response set as well as evaluable for response set. The number and percentage of participants whose best percentage change data is imputed will also be presented.

Best percentage change will be presented graphically using a waterfall plot to present each participant's best percentage change in TL tumour size as a separate bar with the bars ordered from the largest increase to the largest decrease. A reference line at the -30% change in TL tumour size level corresponds with the definition of a 'partial response' and another reference line at the +20% change in TL tumour size corresponds with the definition of 'progressive disease' will be added to the plots. All progressions will be marked with a '●' or designated with patterns or colours for ORR categories. Flagged progression on the best percentage change in TL tumour size at a particular timepoint will be based upon the NTL or new lesion progression at the same timepoint as the best percentage change. The scale in these plots will be fixed to be from -100 to 100 to avoid presenting extreme values. Values that are capped as a result of this restriction to the scale will be marked with '#'. Values are ordered in descending order with imputations due to death appearing first followed by a gap followed by all other participants. Imputed values will be clearly marked with '\*' and participants with imputation where there was a death or evidence of progression will have different shading to each other and the other participants to make it clear that these are different.

Additionally, best percentage change in tumour size will be presented graphically using waterfall plots, where best percentage change in TL tumour size as a separate bar ordered from the largest increase to the largest decrease, colour coded in respective figures by mutation categories/gene variant categories and best objective response categories marked with appropriate symbols on top of each bar.

Additional, 'spider' plots will be produced. This depicts each participant's percentage change in TL tumour size as a line over time and progression due to NTL or new lesions will be indicated (imputed data will not be included in the plots).

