***Missing TL data***

For a visit to be evaluable all TL measurements should be recorded. However, a visit response of PD should still be assigned if any of the following occurred:

- A new lesion is recorded
- An NTL visit response of PD is recorded
- The sum of TLs is sufficiently increased to result in a 20% increase, and an absolute increase of  $\geq 5$  mm, from nadir even assuming the non-recorded TLs have disappeared.

Note: the nadir can only be taken from assessments where all the TLs had a LD recorded.

If there is at least one TL measurement missing and a visit response of PD cannot be assigned, the visit response is NE.

If all TL measurements are missing, then the TL visit response is not evaluable (NE). Overall visit response will also be NE, unless there is a progression of non-TLs or new lesions, in which case the response will be PD.

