### ***Irradiated lesions/lesion intervention***

Previously irradiated lesions (i.e. lesion irradiated prior to entry into the study) should be recorded as NTLs and should not form part of the TL assessment.

Any TL (including lymph nodes), which has had intervention during the study (for example, irradiation / palliative surgery / embolisation), should be handled in the following way and once a lesion has had intervention then it should be treated as having intervention for the remainder of the study noting that an intervention will most likely shrink the size of tumours:

- Step 1: the diameters of the TLs (including the lesions that have had intervention) will be summed and the calculation will be performed in the usual manner. If the visit response is PD this will remain as a valid response category.
- Step 2: If there was no evidence of progression after step 1, treat the lesion diameter (for those lesions with intervention) as missing and if  $\leq 1/3$  of the TLs have missing measurements then scale up as described in the 'Scaling' section below. If the scaling results in a visit response of PD then the participant would be assigned a TL response of PD.
- Step 3: If, after both steps, PD has not been assigned, then, if appropriate (i.e., if  $\leq 1/3$  of the TLs have missing measurements), the scaled sum of diameters calculated in step 2 should be used, and PR or SD then assigned as the visit response. Participants with intervention are evaluable for CR as long as all non-intervened lesions are 0 (or  $<10$  mm for lymph nodes) and the lesions that have been subject to intervention have a value of 0 (or  $<10$  mm for lymph nodes) recorded. If scaling up is not appropriate due to too few non-missing measurements, then the visit response will be set as NE.

At subsequent visits the above steps will be repeated to determine the TL and overall visit response. When calculating the previous minimum, lesions with intervention should be treated as missing and scaled up (as per step 2 above).

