**Scaling**

- If > 1/3 of TL measurements are missing (because of intervention) then TL response will be NE, unless the sum of diameters of non-missing TL would result in PD (i.e. if using a value of 0 for missing lesions, the sum of diameters has still increased by 20% or more compared to nadir and the sum of TLs has increased by  $\geq 5$  mm from nadir).
- If  $\leq 1/3$  of the TL measurements are missing (because of intervention) then the results will be scaled up (based on the sizes at the nadir visit) to give an estimated sum of diameters and this will be used in calculations; this is equivalent to comparing the visit sum of diameters of the non-missing lesions to the nadir sum of diameters excluding the lesions with missing measurements.

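### SAP 4.17.2 does not carry over the 4.9.1 rules on treated or unmeasured target lesions, so a visit scored target-lesion NE can supply the best percentage change in tumour size

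*SAP*

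**What the plan says.** SAP 4.17.2, which serves both cohorts:

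- "Tumour size is the sum of the longest diameters (or short axis measurements for lymph nodes) of the target lesions". Neither scaling nor evaluability is mentioned.
- Change is computed for "The percentage change in target lesion tumour size at each week for which data are available", by "taking the difference between the sum of the target lesions at each week and the sum of the target lesions at baseline", divided by the baseline sum.
- Best change is the largest reduction, or the smallest increase "in the absence of a reduction from baseline based on all post baseline assessments".
- The window closes at the earliest of death without progression, "any evidence of progression, the start of subsequent anti-cancer therapy, or the latest evaluable RECIST assessment" where none of the other events has occurred. The assessment at progression, or the latest evaluable one, is expressly counted.
- If best change cannot be calculated because data are missing, +20% is imputed in listed situations, one of which is new lesions.

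SAP 4.9.1, for target-lesion response:

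- On irradiated, resected or embolised lesions it applies special steps, "noting that an intervention will most likely shrink the size of tumours". Step 1 sums all diameters, treated ones included, to test for progression. Step 2 treats the treated lesions as missing and scales up if at most 1/3 are affected. A treated lesion keeps that status for the rest of the study.
- "If > 1/3 of TL measurements are missing (because of intervention) then TL response will be NE", unless the remaining lesions alone show progression. CR remains possible if every lesion, treated ones included, meets the CR size criteria.
- "For a visit to be evaluable all TL measurements should be recorded"; otherwise the visit is NE unless progression is shown.

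**The concern.** The two sections handle the same measurements differently. For response, the SAP recognises that local treatment shrinks a lesion for reasons unrelated to ceralasertib, and it removes or scales that lesion. For percentage change, 4.17.2 neither repeats nor refers to those rules. A programmer following 4.17.2 as written would sum whatever diameters are recorded.

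Best change is the most favourable value across visits, so one affected visit is enough. The waterfall plot has a reference line at -30% tied to partial response. A bar could pass that line for a participant whose target-lesion response at that visit was NE or SD. With no comparator and about 25 and 27 participants, a single bar is visible and the descriptive summary moves with it.

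**Working it through.** **The plan's own figure.** The scaling example in 4.9.1 gives 28.4 cm: 26/26.8 × 29.3 = 28.43 cm, which reproduces. (The formula works only if 29.3 cm is the full nadir sum, so lesion 5 is 29.3 - 26.8 = 2.5 cm; the text calls 29.3 cm the baseline measure of lesion 5.) Assume the nadir sum equals the baseline sum of 29.3 cm:

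- Partial sum: (26 - 29.3)/29.3 = -11.3%.
- Scaled sum: (28.43 - 29.3)/29.3 = -3.0%.

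The sum chosen changes the answer even on the plan's own numbers.

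The cases below use assumed lesion sizes and the 4.17.2 formula, (visit - baseline)/baseline × 100.

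**Case 1: more than 1/3 treated.** Sole target lesion of 40 mm, embolised, 12 mm at the next scan.

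- 4.9.1: 1/1 > 1/3, so there is no scaled sum. Neither progression nor CR is met, so the response is NE.
- 4.17.2 as worded: (12 - 40)/40 = -70%. The diameter is recorded, so nothing is missing in the ordinary sense.
- Does the window remove it? Without a later event, yes: the lesion stays treated, later visits are also NE, and the latest evaluable assessment precedes the embolisation. If the participant later progresses, dies or starts subsequent therapy, no: the window runs to that event and the NE visit lies inside it.
- If the embolised scan is the only post-baseline visit and shows a new lesion, the overall response is PD, the target lesions are NE and the visit is expressly counted. The literal result is -70%. If the visit is treated as having no usable sum, +20% is imputed. The difference is 20 - (-70) = 90 points for one participant.

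**Case 2: at most 1/3 treated.** Five 20 mm lesions, one irradiated to 5 mm, four unchanged.

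- Unscaled: (85 - 100)/100 = -15%.
- Scaled: 80/80 × 100 = 100 mm, a change of 0%.
- With three 30 mm lesions, one treated to 0 mm and two unchanged: unscaled (60 - 90)/90 = -33.3%, scaled 0%. The bar passes -30% while the target-lesion response is SD.

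**Case 3: a lesion not measured.** Lesions of 30, 30 and 40 mm, the 40 mm lesion not imaged, the others unchanged. The response is NE. Summing only what was recorded gives (60 - 100)/100 = -40%. The text leans against this reading, as discussed under the objection.

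**Direction.** Five 20 mm lesions, one irradiated to 18 mm, four shrunk to 10 mm. Unscaled: (58 - 100)/100 = -42%. Scaled: 40/80 × 100 = 50 mm, so -50%. Here the unscaled sum understates shrinkage.

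**Effect on a summary.** One participant moved from 0% to -70% shifts the mean by -70/25 = -2.8 points, or -70/27 = -2.6 points.

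**The case against.** A reader might infer that the SAP prescribes unscaled sums at every visit and deliberately includes NE visits. It does not: 4.17.2 is silent on both. Several passages favour a sounder reading.

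- The Scaling text says the scaled sum is to be used in calculations. That can be read to reach 4.17.2 when at most 1/3 of lesions are treated. It sits in the response section without a link, though, and cannot help when more than 1/3 are treated, because no scaled sum then exists.
- SAP 4.3.3 does not impute missing data, and 4.17.2 foresees a best change that cannot be calculated and refers to evaluable target-lesion data. This weighs against Case 3. But the reference to evaluable data appears only in a condition for imputation and does not select visits.
- The latest-evaluable-assessment limit removes Case 1 for participants with no later event. That stands, and the point is confined accordingly.
- On-study local treatment might itself count as subsequent anti-cancer therapy, which would close the window. The SAP does not say, and 4.8 refers to the protocol for anti-cancer treatments. If it does count, most treated-lesion cases disappear.
- The additional waterfall plots mark best objective response on each bar, so a mismatch could be seen. That helps a reader of those figures but does not correct the summary statistics.

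**Conclusion.** The point holds as a gap in 4.17.2 whose literal wording admits values that 4.9.1 calls non-evaluable. It is firmest when more than 1/3 of target lesions are locally treated and measured, in a participant who later progresses, dies or starts subsequent therapy, or at a progression visit with target lesions NE. For at most 1/3 treated it is an unresolved choice between two sums. For unmeasured lesions it is an omission that the surrounding text partly answers.

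Three stronger inferences are not supported. The error is usually, not always, toward shrinkage, as the -42% versus -50% example shows. ORR is not inflated, because it follows 4.9.1. The mean shift for Cohort B need not use 27: Table 4 admits participants on an unfavourable CTC count without measurable disease, so fewer may contribute a target-lesion sum.

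The size per affected participant can be large (-70% at an NE visit, or -15% versus 0%), on assumed lesion sizes. The number affected is not in the document, and the overall effect is small if interventions and incomplete visits are rare. The endpoint is secondary and descriptive, with no hypothesis test (4.10). A correction is still worthwhile because it costs so little.

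**What to change.** Add to SAP 4.17.2, for percentage change, best percentage change, and the waterfall and spider plots:

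1. Only visits with an evaluable target-lesion response, or an evaluable target-lesion sum at progression, contribute.
2. Where at most 1/3 of target lesions have had an intervention, the scaled sum from 4.9.1 is used.
3. Where 4.9.1 assigns CR with treated lesions, the recorded sum is used.
4. Other visits with target-lesion response NE do not contribute. If no value remains, the existing +20% rule applies where its conditions are met; otherwise best change is missing.

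The cost is SAP wording and reuse of sums already derived for response. A few participants may have fewer usable visits, or a missing or imputed value; 4.17.2 already reports how many values are imputed.
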